The Alpert Jewish Family and Children's Service, West Palm Beach currently serves approximately 205 people who receive peer to peer support. There is not currently a waiting list so we will be recruiting people out of the community to serve as the control group. All people in both groups have access to all other services that the Jewish Family and Children's Service offers older adults in the community. People receiving peer to peer support will receive ID Numbers PB100E to PB499E and people receiving standard community services (on the wait list to receive peer to peer support) will receive ID numbers PB500C to PB999C.

A list of participants that are currently receiving peer to peer support will be uploaded into DatStat. However, only first name, age, date of birth, gender and race will be uploaded into the system. The Research Staff will keep a separate list of contact information for these participants on a secure file on her computer. Once a participant agrees to be in the study, then the additional contact information (phone number, address, last name) will be added into DatStat.

- A. One recruitment strategy will be to contact people off of a pre-specified list of people receiving peer to peer support. These people are already receiving services from the Jewish Family and Children's Service. We will send out letters to the first 10 people on the list. The letter will give them the option to call us but it will also let them know that we will be calling them within the next two weeks to see if they are interested in participating in the research study. Research staff will select the next person to call based on the number of people they are trying to recruit in each of the pre-specified categories (ex: white women 65-70). The biostatisticians have created a list of the number of people we should recruit in each demographic bucket based on the demographic breakdown of the people currently receiving peer to peer support. We will then send out the *Introductory Letter* to potential participants from the sessions (on the "wait list") and to potential participants currently receiving peer to peer support. We will send out eligibility letters to people enrolled in peer-to-peer support and to those who are eligible for peer to peer services simultaneously. Every 2-3 weeks we will send letters to 20 new people.

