- B. We are also going to hold informational sessions for the purpose of recruiting eligible participants for the study creating our "waitlist". These sessions will be held in three adult gated communities – Century Village, Golden Lakes and Banyan Springs and also our sister agencies. We will then send out the *Introductory Letter* to potential participants from the sessions (on the "wait list"). Alternatively, we will collect demographic information from participants at the information sessions and if it is feasible we may even conduct screenings on site.

We will send out eligibility letters to people enrolled in peer-to-peer support and to those who are eligible for peer to peer services simultaneously. Every 2-3 weeks we will send letters to 20 new people.

Recruitment Goal: As of September 3, 2015 the new recruitment goal at Jewish Family Services of Palm Beach will be to recruit 300 participants into the study (150 experimental and 150 control)

Jewish Family Service of LA

Jewish Family Service of Los Angeles (JFSLA) currently has 57 people receiving peer to peer support and 35 people on the wait list to receive peer to peer support. They are actively expanding their program. All people in both groups have access to all other services that JFSLA offers older adults in their community such as case management, mental health services, link to community resources, meals, and transportation.

A list of participants receiving peer to peer support will be uploaded into DatStat

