Randomization and matching In order to reduce potential bias further, participants from the AJFCS of Palm Beach will be allocated either to peer-to-peer support (Intervention) or standard community support (Control) in a 1:1 ratio using permuted block randomization, stratified by age, gender and race/ethnicity. Barring randomization in JFS of LA and Community Place of Greater Rochester, older adults already participating in peer-to-peer support and those on the waiting list will be matched on age, gender and race/ethnicity to mitigate potential differences between the two groups. In order to avoid reporting/ascertainment bias, calls will be made to all participating older adults and support staff at 3 and 9 months as outlined in Figure 4 above.

Sample Size Justification Given the total sample size of 720 at-risk older adults, the study has 0.80/0.85/0.90 power to detect the effect size of 0.209/0.223/0.242 for the primary outcome measure of the annualized rate of hospitalization, ED use and institutionalization at a two-tailed significance level 0.05. The effect size here is defined as the difference in the mean annualized rate of hospitalization, ED use and institutionalization between the two groups divided by the standard deviation of the annualized rate assumed to be common in the two groups. Due to random drop-out or loss to competing event of death, the study will have less power to detect the stated effect sizes or will have the stated power for larger effect sizes.

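### The SAP randomises the Palm Beach site (AJFCS), but the protocol forms its groups from current recipients and matched community controls; analyses 2 and 3 depend on which text holds

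*SAP*

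**What the plan says.** **SAP.** Under Randomization and matching, "participants from the AJFCS of Palm Beach will be allocated either to peer-to-peer support (Intervention) or standard community support (Control) in a 1:1 ratio", by permuted blocks stratified by age, gender and race/ethnicity. The next sentence gives the other two sites a different design: "Barring randomization in JFS of LA and Community Place of Greater Rochester, older adults already participating in peer-to-peer support" are to be matched with people on the waiting list. The Analysis Plan builds on this split. Analysis 2 checks whether the randomised and non-randomised parts agree and whether their effects differ in size. Analysis 3 uses AJFCS alone to compare 12 with 6 months of peer support, with the AJFCS controls moving to peer support at month 6.

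**Protocol.** The AJFCS part of Recruitment Strategies describes a different process:
- The experimental group is contacted from a list of people already receiving peer support.
- For controls: "There is not currently a waiting list so we will be recruiting people out of the community to serve as the control group".
- The site adds: "We are also going to hold informational sessions for the purpose of recruiting eligible participants for the study creating our" waitlist.
- Study codes follow service status: "People receiving peer to peer support will receive ID Numbers PB100E to PB499E and people receiving standard community services" receive the C codes.
- Recruitment works to a target, the "number of people we should recruit in each demographic bucket based on the demographic breakdown of the people currently receiving peer to peer support".

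The Matching section names AJFCS, with Community Place, as matched on age group, gender and race/ethnicity. It adds that at all sites people from the waiting list are matched with current recipients.

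**The concern.** A person who already receives peer support cannot be randomised to start it. A group recruited afterwards, to resemble current recipients, is not a randomised control group. The two texts therefore describe different studies at the site with the largest recruitment goal.

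If the SAP is applied to data collected as the protocol describes, a matched comparison will be reported as randomised evidence. Agreement between AJFCS and the other sites would then be read as experimental support for the quasi-experimental result, when both sides share the same weakness. If the SAP's design was followed, the protocol misdescribes how the AJFCS arms were formed.

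**Working it through.** **The plan's own figure.** The SAP's sample size statement begins "Given the total sample size of 720 at-risk older adults". With 360 per arm, two-sided 0.05 and a common SD, power at effect sizes 0.209, 0.223 and 0.242 is 0.801, 0.849 and 0.901. This reproduces the stated 0.80, 0.85 and 0.90 and is not in dispute.

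**What is at stake in numbers.** The protocol's site goals are Community Place 226, AJFCS 300 and JFS of LA 60: 226 + 300 + 60 = 586. The number randomised is then 300 of 586 if AJFCS is randomised, and 0 of 586 if it is not. The SAP gives no AJFCS number of its own.

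**The two texts on AJFCS, side by side.**
- Source of the intervention arm. SAP: random allocation. Protocol: a list of current recipients.
- Source of the control arm. SAP: random allocation. Protocol: community recruits.
- Matching. SAP: the other two sites only. Protocol: AJFCS named, and matching to current recipients stated for all sites.
- Month 6. SAP: controls move to peer support. Protocol as supplied: no such move described.
- Random draws. The only one in the supplied protocol picks one member of a couple; it does not assign an arm.

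**Consequences if the protocol's conduct stands.**
1. Analysis 2 compares one non-randomised component with another.
2. Analysis 3 has no randomised arms. The Consent and Baseline Visit section puts time zero at consent, but recipients were exposed before consent, so baseline to month 12 is not 12 months from the start of support.
3. The primary two-sample tests, which are unadjusted, are non-randomised at every site.

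**Analysis 3 under either text.** Let d1 and d2 be the changes common to both arms over months 0–6 and 6–12, and E12 and E6 the effects of 12 and 6 months of support. For measures taken at a visit (self-rated health, wellness, depression, anxiety):

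(d1 + d2 + E12) − (d2 + E6) = (E12 − E6) + d1.

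The common change d1 remains and would be read as an effect of duration. Over the same 0–12 interval in both arms:

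(d1 + d2 + E12) − (d1 + d2 + E6) = E12 − E6,

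and the common change cancels.

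Utilisation and placement are rates over intervals, and the SAP does not define the change in rate precisely. On one reading (rate over months 0–12 in one arm, over 6–12 in the other), with common half-year rates r1 and r2, the leftover term is (r1 + r2)/2 − r2 = (r1 − r2)/2. That differs from d1 and may have the opposite sign. So a common trend does not cancel in general, but its form depends on the definition. The documents give no figure for change over months 0–6, so no size can be put on it.

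**The case against.** **The SAP is later and should govern.** Its file carries the date 10/30/2017, while the AJFCS goal is introduced with "As of September 3, 2015 the new recruitment goal at Jewish Family Services of Palm Beach". But that SAP still plans 720, while the protocol's 2015–2016 goals total 586, so the later date does not show that it reflects conduct. No text ranks one document over the other.

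**The supplied file is incomplete.** Some pages were removed, figures are not shown, and survey procedures sit in separate documents. This stands against any claim that rests on silence, such as the missing month-6 move. It does not touch the contradiction, which lies between statements that are present.

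**Stronger readings that the documents do not support.**
- A reader might infer that 42–51% of the study is randomised if the SAP holds (300/720 or 300/586). The 300 comes from the protocol text that conflicts with the SAP, and 300/720 implies 420 at the other sites, where the protocol's goals give 226 + 60 = 286. All of AJFCS or none is what can be said.
- A reader might add that analysis 2 is too imprecise, since the difference between components has an SE of about 0.165 SD (300 and 286) or 0.151 SD (300 and 420). That arithmetic is right, but it is the same under either design and says nothing about which text holds. Nor is 0.209 a planned effect to judge it by: the SAP gives it as the effect detectable with 0.80 power.
- A reader might apply the d1 result to every outcome. It is shown only for measures taken at a visit.

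**Conclusion.** The contradiction is real, and no reading of the current texts reconciles it. It must be fixed, because it decides whether the study has any randomised component: 300 of 586 by the protocol's goals, or none. The 300 is a recruitment goal, not an enrolled number.

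A reader might conclude that AJFCS was in fact not randomised. The documents do not show that; they show two incompatible accounts. The losses listed for analyses 2 and 3 and the primary tests are conditional on the protocol's account being the true one.

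The unequal intervals in analysis 3 are a separate flaw that holds under both accounts. Its size is unknown.

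**What to change.** State how the AJFCS groups were actually formed, and reconcile the protocol's AJFCS recruitment and matching text with the SAP's Analysis Plan and Randomization and matching text.

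**If the protocol's conduct stands:**
- Describe all three sites as a non-randomised matched comparison.
- Report analysis 2 as the AJFCS-versus-other-sites difference in effect with a 95% CI, not as a check of one design against the other.
- Drop analysis 3 as a randomised dose comparison.
- Make the regression that the SAP already plans the primary analysis. Adjust for the matching factors, site, county at Community Place, and baseline confounders named in advance from those the trial collects.
- Say that confounding between current recipients and community recruits may remain. The matching factors are largely balanced already, so adjusting for them will not remove it.

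The cost is SAP text and the promotion of a planned model. The claim to a randomised component is lost.

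**If the SAP's design stands:**
- Rewrite the AJFCS recruitment, ID and matching text to describe the randomisation.
- Replace analysis 3 with a comparison of the randomised arms over the same baseline-to-12-month interval, labelled early versus delayed start.

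The cost is a rewrite of the AJFCS procedures, and the duration question gives way to one about timing of start.

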For Community Place and Alpert Jewish Family and Children's Service (AJFCS), we are matching participants on the following characteristics: age group (<70, 70-80, and ≥ 80 years), gender (male and female), race/ethnicity (African American, Hispanic, and non-Hispanic White) and at Community Place we are also matching based on County (Monroe or Livingston).

At both all sites we are going to recruit people from the waiting list and match them with people already receiving peer to peer services. Every month research staff at UW will ask to see the matching spreadsheet as a way to monitor how matching is progressing at each site.

Enrolling more than one person per household (added 1/14/2016)

As of February 22, 2016, we will only enroll one person per household. This is the protocol for determining which person from the household we will enroll.

- a. If Participant A is enrolled in the study (signed the consent form) and they say they would like their partner would like to participate, the research staff person will let them know that according to study protocol we are only allowed to enroll one person per household. Participant A will be the person that is enrolled in the study.
- b. If prior to enrollment a study staff person is informed that both partners in a couple want to participate in the study. The staff person will let the two participants know that we can only enroll one participant from the couple. If we only need one person then the research staff will screen and enroll that person.
- c. If we know in advance there is a couple interested in participating and both people are needed for the study then we will randomly select one person per household. In this case you should screen both participants. If both participants are deemed eligible to participate you should first assign one participant heads and one participant tails. Then you should pull out the randomization envelope and open it. This envelope will tell you which participant you will enroll. At this time you will discard the envelope.

Enrollment in Study

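### The SAP randomises AJFCS in strata of age, gender and race/ethnicity, but the protocol recruits two ready-made groups there and matches them on the same factors; reconcile the two, and conceal allocation if randomisation stands

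*SAP*

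**What the plan says.** **SAP.** Under Randomization and matching, AJFCS participants go to peer support or standard services "in a 1:1 ratio using permuted block randomization, stratified by age, gender and race/ethnicity". Matching is described only for JFS of LA and Community Place, as the substitute for randomisation there. Under Analysis Plan, analysis 2 sets AJFCS against the other two sites as randomised versus non-randomised designs. Analysis 3 uses AJFCS alone and refers to its groups as randomised.

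**Protocol.** In the AJFCS recruitment section, one strategy is to "contact people off of a pre-specified list of people receiving peer to peer support". With no waiting list at the site, controls are to be recruited from the community, through information sessions. ID numbers carry E for people receiving peer support and C for people receiving standard services. On the order of approach, "Research staff will select the next person to call based on the number of people they are trying to recruit" in each demographic category. The Matching section begins: "For Community Place and Alpert Jewish Family and Children's Service (AJFCS), we are matching participants on the following characteristics". These are age group, gender and race/ethnicity, with county added at Community Place only. It then extends matching to all sites and adds: "Every month research staff at UW will ask to see the matching spreadsheet as a way to monitor how matching is progressing at each site".

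Neither document states a block size, who holds an allocation list, or how assignments are concealed. The only randomisation envelope in the protocol text chooses one member of a couple.

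**The concern.** The two documents give AJFCS incompatible ways of forming its groups. If people enter the peer-support group because they already receive peer support, their group is fixed before the first call and nothing is left to randomise. If they are randomised, they cannot be drawn from a recipient list and a separate community pool, and matching the arms has no role.

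The choice decides what AJFCS can support. Analysis 2 uses it as the randomised component against which the other sites are compared. Analysis 3 treats its two groups as randomised. Without randomisation, AJFCS is a third matched comparison and both analyses need restating.

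There is a second-order risk. Suppose the conflict is settled in favour of the SAP but the protocol's matching text stays. Site staff would then be tracking matching on the three factors that define the randomisation strata, while also choosing whom to approach by demographic category. If their tally showed counts by arm within cell, the next assignment would be partly predictable. The primary test is an unadjusted two-sample comparison, so any steering of candidates would not be corrected there.

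**Working it through.** **Step 1: the passages side by side.**

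| Item at AJFCS | SAP | Protocol |
|---|---|---|
| How group is determined | 1:1 permuted blocks | Current recipients from a list; controls from the community |
| Age, gender, race/ethnicity | Randomisation strata | Matching factors |
| Where matching applies | The other two sites only | Community Place and AJFCS named; then all sites |
| When group is known | Not stated | Before contact, from receipt of peer support |
| Block size, concealment | Not stated | No arm randomisation described |

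The first and third rows cannot both be followed as written. Dates do not settle it: the AJFCS goal is dated September 2015 and the SAP title page October 2017, but neither text says it supersedes the other.

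**Step 2: how much of the trial is affected.** The protocol's site goals are 226 (Community Place), 300 (AJFCS) and 60 (JFS of LA). 226 + 300 + 60 = 586, so AJFCS is 300/586 = 51%. Against the SAP's total of 720 it would be 300/720 = 42%.

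The plan's only calculation is power. With 360 per arm, power = Φ(d√(360/2) − 1.96), which gives 0.801, 0.849 and 0.901 at d = 0.209, 0.223 and 0.242. The stated 0.80/0.85/0.90 reproduce and are not in dispute here.

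**Step 3: predictability, only if AJFCS is randomised and counts by arm within cell are visible.** The protocol's categories give 3 × 2 × 3 = 18 cells, averaging 300/18 = 16.7 people. Block sizes below are assumptions. Take the rule: guess the arm that is behind in the cell, toss a coin at ties. For a block of 2m the expected share of correct guesses is

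[m + (4^m / C(2m, m) − 1)/2] / (2m).

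- Block 2: [1 + (4/2 − 1)/2]/2 = 0.750
- Block 4: [2 + (16/6 − 1)/2]/4 = 0.708
- Block 6: [3 + (64/20 − 1)/2]/6 = 0.683
- Block 8: [4 + (256/70 − 1)/2]/8 = 0.666
- Block 16 (about a whole average cell): [8 + (65536/12870 − 1)/2]/16 = 0.628

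Chance is 0.50. Full enumeration of blocks of 2, 4, 6 and 8 gives the same values. The rule needs the current counts but not the block size. In simulated cells of 16 with blocks randomly varied among 4, 6 and 8, it was still right about 67% of the time. Varying blocks alone therefore does not help much while the counts are visible.

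**Step 4: under the protocol's procedure.** Group follows from whether the person already receives peer support, so there is no sequence to guess and Step 3 does not apply.

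**The case against.** The strongest objection is that predictability arises only by combining half of each document: under the SAP AJFCS is outside the matching, and under the protocol it is not randomised. That stands. It is why the contradiction is the point and the guess rate is conditional on how it is resolved.

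A reader might infer more than the documents support:

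- **That the tally and call rule reveal the sequence as written.** The AJFCS call rule names no group. The spreadsheet's columns are not described; that it shows both groups by cell is a reasonable guess from its purpose, no more. The E and C labels are ID ranges, and the only targets by group are the site totals of 150 and 150.
- **That strata and matching cells are identical.** The factor names agree, but the SAP gives no cut-points for its strata. The same age bands appear only in its subgroup paragraph, and the protocol's example category of ages 65-70 does not fit them exactly.
- **That a bias can be quoted in SD units.** The documents give no figure for steering. Letters go out in batches of 10 or 20 every two to three weeks, with up to three weekly call attempts, so counts may have moved between choosing a candidate and allocation. For listed recipients, DatStat at first holds first name, age, date of birth, gender and race, with no health data.

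Some mitigation is planned. Later regressions adjust for stratification factors and other confounders, and analysis 3 compares changes over time. Neither settles whether AJFCS was randomised.

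One might also try to harmonise the texts by reading the demographic categories as recruitment quotas applied before randomisation. The call rule alone would bear that, but the recipient list, the community controls and the naming of AJFCS as a matching site would not.

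**Conclusion.** The point holds as a contradiction that must be resolved. The SAP and protocol cannot both govern AJFCS, which supplies 300 of the 586 planned participants on the site goals and is the only component the SAP calls randomised. Analyses 2 and 3 cannot be interpreted as described until this is settled.

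Predictable allocation is a conditional risk. It needs randomisation to be in force and recruiters to see up-to-date counts by arm within cell. On those assumptions the lagging-arm guess is right about 63% to 75% of the time for blocks from 16 down to 2. No bias or type I error figure follows from the documents. Missing block size and concealment details alone would be a gap in reporting, not a demonstrated flaw.

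**What to change.** Decide which account is right, and amend both documents to match.

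**(a) If AJFCS is randomised.** Remove AJFCS from the protocol's Matching section, and remove the recipient-list and community-control recruitment from its AJFCS section. State that UW holds the allocation list, uses randomly varied block sizes not disclosed to the site, and releases each assignment only after consent and the baseline survey. Give AJFCS recruiters no running counts by arm within cell; UW monitors balance. If enrolment is already complete, check whether baseline health is associated with the within-cell imbalance just before each entry, and report a sensitivity estimate adjusted for that imbalance.

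**(b) If AJFCS was not randomised.** Delete the permuted-block sentence from the SAP. Deleting it alone is not enough: revise Analysis Plan so that analysis 2 no longer treats AJFCS as a randomised benchmark and analysis 3 no longer refers to randomised groups.

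**Cost.** Mainly wording in both documents and no added participants. Route (a) also needs a central release step, for which the documents describe no mechanism. The site would rely on UW to monitor balance, and staff who know individual assignments could still guess to some extent.

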- A. One recruitment strategy will be to contact people off of a pre-specified list of people receiving peer to peer support or on the wait list to receive peer to peer support. These people are already receiving community services from Community Place. We will send out letters to the first 10 people on the list. The letter will give them the option to call us but it will also let them know that we will be calling them within the next two weeks to see if they are interested in participating in the research study. Research staff will select the next person to call and recruit to the study in the recruitment pattern according to the matching strategy that the biostatisticians prepared based on the sociodemographic breakdown of the clientele that are currently receiving peer to peer support. We will send out the *Introductory Letter* to potential participants on the wait list and to potential participants currently receiving peer to peer support. We will send out eligibility letters to people enrolled in peer-to-peer support and on the wait list simultaneously. Every 2-3 weeks we will send letters to 10 new people.
- B. A second recruitment strategy will be by making an announcement about the study at monthly training meetings for both Foster grandparent and senior companion programs. After the announcement is made, the research coordinator will approach potential participants at monthly training meetings and ask them if they are interested in learning more. If interested, we will tell them about the study, screen them for eligibility send them home with a consent form and set up a time to conduct the baseline interview. There is the possibility of enrolling 15-20 people at this meeting. This meeting occurs every month.
- C. A third recruitment strategy will be to hold informational sessions for the purpose of recruiting eligible participants for the study creating our "waitlist". These sessions will be held at community centers around town and in other venues where older adults frequent.

D. Community Place will be partnering with Star Program to recruit additional peers.

Recruitment Goal: As of February 23, 2016 the new recruitment goal at Community Place will be to recruit 226 participants into the study (113 experimental and 113 control)

Alpert Jewish Family and Children's Service

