- A. One recruitment strategy will be to contact people off of a pre-specified list of people receiving peer to peer support or on the wait list to receive peer to peer support. These people are already receiving community services from JFS of LA. We will send out letters to the first 10 people on the list. The letter will give them the option to call us but it will also let them know that we will be calling them within the next two weeks to see if they are interested in participating in the research study. Research staff will select the next person to call and recruit to the study in the recruitment pattern according to the matching strategy that the biostatisticians prepared based on the sociodemographic breakdown of the clientele that are currently receiving peer to peer support. We will send out the *Introductory Letter* to potential participants on the wait list and to potential participants currently receiving peer to peer support. We will send out eligibility letters to people enrolled in peer-to-peer support and on the wait list simultaneously. Every 2-3 weeks we will send letters to 10 new people.
- B. A second recruitment strategy will be to recruit from Park LaBrea and/or meal programs that are put on by JFS of LA.

Recruitment Goal: As of February 23, 2016 the new recruitment goal at Jewish Family Services of Los Angeles will be to recruit 60 participants into the study (30 experimental and 30 control).

Contacting Potential Participants via the Telephone Prior to Enrollment in the Study (If we are unable to reach a potential participant via telephone, we will leave the following message.)

Hello {U:DATSTAT_FIRSTNAME}. My name is {U:RA_FIRST} {U:RA_LAST} from {U:DATSTAT_SITE}. I am calling to see if you would like to participate in a survey research study to better understand what helps older adults stay in their homes and communities. If you are interested in learning more about the Aging in Place study please call me back at {U:RA_TELEPHONE} and leave me a message if I'm not at my desk. Otherwise, I will call you back in one week to talk with you. If you are not interested in receiving any more calls from me about this study, please call me and let me know and I will not contact you again. Again, my name is {U:RA_FIRST} and my phone number is {U:RA_TELEPHONE} and I look forward to talking with you soon. Have a great day.

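### The SAP's power statement assumes 720 participants, but the protocol's current site goals total 586, so the planned sample does not give the stated power.

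*SAP*

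**What the plan says.** The SAP's Sample Size Justification is the only power statement in the documents. It reads: "Given the total sample size of 720 at-risk older adults, the study has 0.80/0.85/0.90 power to detect the effect size of 0.209/0.223/0.242". The claim is for the primary outcome, the annualized rate of hospitalization, ED use and institutionalization, with a two-tailed 0.05 test. The effect size is the difference in mean annualized rates "divided by the standard deviation of the annualized rate assumed to be common in the two groups". The section then adds that drop-out and death will lower the power or raise the detectable effect. It gives no loss rate and no other cause.

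Under Recruitment Strategies, the protocol sets a revised goal for each site:

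- Community Place, as of February 23, 2016: "recruit 226 participants into the study (113 experimental and 113 control" participants.
- Alpert Jewish Family and Children's Service (AJFCS), as of September 3, 2015: "recruit 300 participants into the study (150 experimental and 150 control" participants.
- Jewish Family Service of LA, as of February 23, 2016: "recruit 60 participants into the study (30 experimental and 30 control" participants.

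The SAP's Analysis Plan describes the main comparison as pooling all three sites, so the power statement should rest on the sum of these three goals. The SAP's opening page carries a protocol version date of 10/30/2017, later than all three revisions.

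**The concern.** The two documents give different sizes for the same trial, and the power statement uses the larger one. If the site goals are what the trial set out to recruit, the stated power at the stated effect sizes does not belong to this study. The SAP's caveat does not help, because it concerns participants lost after enrolment and the gap here arises before anyone is lost.

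The consequence lies mainly in interpretation. A reader facing a null primary result would take from the SAP that a difference of 0.209 SD had an 80% chance of being detected. At the planned recruitment the chance of missing that difference is about 29%, before any attrition.

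**Working it through.** **Inputs.** From the SAP's Sample Size Justification: N = 720; power 0.80/0.85/0.90; standardized effects 0.209/0.223/0.242; two-tailed alpha 0.05; common SD. From the protocol's Recruitment Strategies: site goals of 226, 300 and 60, each split equally between the groups. The test is a two-sample comparison of means, one of the primary tests the SAP lists. Equal group sizes are assumed for 720; the reproduction in step 1 supports this.

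**Step 1: reproduce the SAP's figures.** The detectable effect is d = (1.960 + z_power) × √(2/n), with n per group and z_power = 0.842/1.036/1.282. For n = 360, √(2/360) = 0.07454, so

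- 0.80: 2.802 × 0.07454 = 0.2088
- 0.85: 2.996 × 0.07454 = 0.2233
- 0.90: 3.242 × 0.07454 = 0.2416

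These round to 0.209/0.223/0.242, exactly as stated. A one-sided test would give power of 0.877/0.911/0.945 and does not match. The SAP's figures therefore come from 360 per group, two-sided, with no allowance for loss.

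**Step 2: sum the site goals.** 226 + 300 + 60 = 586, and 113 + 150 + 30 = 293 per group. 720 − 586 = 134, and 586/720 = 0.814.

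**Step 3: recompute at 293 per group.** √(2/293) = 0.08262, so the same formula gives 0.2315/0.2476/0.2678. The ratio to the SAP's values is √(720/586) = 1.108, about 11% larger.

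Power is approximately Φ(d√(n/2) − 1.960). For d = 0.209, 0.209 × √146.5 = 2.530, and Φ(0.570) = 0.716. For 0.223 and 0.242 the results are 0.770 and 0.834.

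The noncentral t distribution gives nearly the same answers: power 0.714/0.769/0.833 and detectable effects 0.2318/0.2480/0.2683. The noncentral t values are used in the conclusions.

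**Step 4: add attrition.** The documents give no rate, so 10% and 20% are assumptions to show a range (noncentral t):

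| Analysed | Power at 0.209 | Detectable effect at 0.80 power |
|---|---|---|
| 720 (SAP) | 0.80 | 0.209 |
| 586 (site goals) | 0.71 | 0.232 |
| 527 (586 less 10%, assumed) | 0.67 | 0.244 |
| 469 (586 less 20%, assumed) | 0.62 | 0.259 |

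At the assumed 20% loss, the detectable effects for 0.80/0.85/0.90 power are 0.259/0.277/0.300.

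Like the SAP's own statement, these calculations ignore matching and any clustering by site.

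**The case against.** The strongest reply is that the SAP sentence is conditional on 720 and is correct on that condition. 720 was presumably the design size before the site goals were revised, and parts of the statistical text read as carried over from a proposal. The date on the SAP is labelled a protocol version date, so it does not prove that anyone reaffirmed 720 after the revisions. Neither document states an overall total of 586, and neither reports actual enrolment. The fall in power is moderate, no test or endpoint is affected, and a null result is better judged from its confidence interval than from planned power.

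Much of this is fair as description. The SAP's formula is not wrong; its N is out of line with the protocol. The documents do not show that the trial was undersized from the outset. 80% power is still available at 586, but for effects of about 0.232 or more.

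None of it removes the conflict. Carried-over text explains how the mismatch may have arisen but does not make the statement true of the current plan. The goals are worded as totals to recruit into the study, so they are neither top-ups nor counts of completers. The SAP's pooled analysis names three sites, and the protocol gives goals for those same three. The drop-out caveat points in the right direction but concerns a different and additional loss.

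**Conclusion.** The point stands: the power statement is wrong as written for the recruitment the protocol plans. At 586, power for 0.209/0.223/0.242 is 0.71/0.77/0.83, a loss of 7 to 9 percentage points, and the effects detectable at 0.80/0.85/0.90 power are 0.232/0.248/0.268. The shortfall equals an 18.6% loss before follow-up begins.

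This rests on reading the three site goals as the current totals, on equal groups, and on a two-sided 0.05 comparison of means. It concerns the planned sample, since actual enrolment is not reported. The figures at 10% and 20% loss depend on assumed rates.

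**What to change.** In the SAP's Sample Size Justification, replace 720 with 586 (293 per group) and give detectable effects of 0.232/0.248/0.268 at 0.80/0.85/0.90 power. State an attrition assumption with its basis and repeat the figures after that loss; at 20%, for example, they would be 0.259/0.277/0.300. Note that the target was reduced through the site goals, so that the drop-out caveat is not taken to cover it. If there is a documented reason to keep 720, the SAP should give it and the protocol's site goals should be reconciled with it.

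Restating the figures costs SAP wording only. It requires no extra enrolment and no change to endpoints or tests. The price is a less favourable stated power.
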